8.2 MOAKS MRI Assessments

The MOAKS variables below will be listed for each patient.

MOAKS Variables

- Bone Marrow Lesions (BMLs) and cysts (15 regions)
 - Number of BML cyst
 - Size of BML
 - % that is BML
- Cartilage Assessment (14 regions)
 - Size of any Cartilage Loss: 0='Normal', 1='<10% Area', 2='10-75% Area', 3='>75% Area', 9='Not Evaluable'
 - Percentage Full Thickness Loss: 0='Normal', 1='<10% Region', 2='10-75% Region', 3='>75% Region', 9='Not Evaluable'
- Osteophytes (12 regions): 0='None', 1='Small', 2='Medium', 3='Large', 9='Not Evaluable'
- Hoffa-Synovitis: 0='None', 1='Mild', 2='Moderate', 3='Severe'
- Effusion-Synovitis: 0 = 'Physiologic Amount', 1 = 'Small', 2 = 'Medium', 3 = 'Large'

For each patient and visit, the number of subregions/locations impacted by a MOAKS MRI feature will be calculated for the following variables:

- Number of BMLs and cysts.
- Size of any Cartilage Loss.
- Osteophytes

A subregion/location is considered to be by the MRI feature if it has score =1 or higher.

Shift tables by group will be tabulated for the shift from baseline to visit 5 for the number of subregions impacted by the MRI feature for the three MOAKS variables above.

PAREXEL International Statistical Analysis Plan

Medivir
Protocol: MIV-711-202

Final 1.0
16 January 2018

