All pre- and post-dose assessments including unscheduled assessments will be included in the data listings. For unscheduled assessments collected pre-dose, the last assessment taken for a time point will be used in the data summaries (summary tables, figures, and statistical analysis); for all post-dose time points, the original assessment for any given time point will be used in the data summaries (summary tables, figures, and statistical analysis).

Descriptive statistics for observed values and derived change from baseline values will be tabulated by visit and study group. Continuous variables will be summarized by study group and visit, as appropriate, using descriptive statistics including: number of observations (n), mean (arithmetic), median, standard deviation (SD), minimum, and maximum. Frequencies and percentages will be used for summarizing discrete (categorical) data by study group and visit, as appropriate. The denominator used when calculating percentages will be the number of patients assessed at a particular combination of study group and study visit, as appropriate.

Safety and efficacy data that are reported as missing will be excluded from all descriptive and non-descriptive data analysis. There will be no imputation of any data. Observations that might be considered spurious (extreme relative to the majority of the data) will not be altered or removed from any presentation of the data, including the calculation of summary statistics (means, medians, etc.), unless approved by the sponsor.

For data listings, all raw data will be reported/displayed exactly as provided. For summaries of quantitative safety data, the minimum and maximum value will be reported exactly as the raw data are reported; measures of central tendency (means, medians) will be reported to one more decimal place than the raw data; measures of variance (SD) will be reported to two more decimal places than the raw data.

Unless stated otherwise there will be no adjustment for multiple comparisons.

PAREXEL International Statistical Analysis Plan

Medivir
Protocol: MIV-711-202

Final 1.0
16 January 2018

In all data presentations ‘Treatment’ will be defined as 200 mg MIV-711. Listings will include all patients and will be sorted by patient number and time point (where applicable). All derived data used in a data summary or statistical analysis will be listed.

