[1] for each examination test, the summary will consider all possible subregions associated with BML and Cyst. Maximum number of subregions is 15. In this analysis a subregion is said to be affected by a BML if the MRI score > 0. A subregion is not affected by any BML if that subregion is scored as 0.

Programming note: table will include summaries for each MOAKS test: Number of BMLs, Size of BML, % that is BML. Follow-up data will be excluded from all MOAKS table summaries.

PAREXEL International SAP Amendment Shells

Medivir
Protocol: MIV-711-202

Final 1.0
16 January 2018

Medivir
Protocol Number: MIV-711-202

Page X of Y

Table 14.2.2.2
Imaging variables - MOAKS Cartilage Assessments Size of any cartilage loss
Shift from Baseline to Visit 5 Number of Subregions Impacted by MRI Feature, ITT Population

Group	Number of subregions affected [1]	Baseline									
		0	1	2	3	4	5	6	7	8+	
A N = x	0	nn (nn.n%)	nn (nn.n%)	nn (nn.n%)	nn (nn.n%)	nn (nn.n%)	nn (nn.n%)	nn (nn.n%)	nn (nn.n%)	nn (nn.n%)	nn (nn.n%)
	1	nn (nn.n%)	nn (nn.n%)	nn (nn.n%)	nn (nn.n%)	nn (nn.n%)	nn (nn.n%)	nn (nn.n%)	nn (nn.n%)	nn (nn.n%)	nn (nn.n%)
	2	nn (nn.n%)	nn (nn.n%)	nn (nn.n%)	nn (nn.n%)	nn (nn.n%)	nn (nn.n%)	nn (nn.n%)	nn (nn.n%)	nn (nn.n%)	nn (nn.n%)
	3	nn (nn.n%)	nn (nn.n%)	nn (nn.n%)	nn (nn.n%)	nn (nn.n%)	nn (nn.n%)	nn (nn.n%)	nn (nn.n%)	nn (nn.n%)	nn (nn.n%)
	4	nn (nn.n%)	nn (nn.n%)	nn (nn.n%)	nn (nn.n%)	nn (nn.n%)	nn (nn.n%)	nn (nn.n%)	nn (nn.n%)	nn (nn.n%)	nn (nn.n%)
	5	nn (nn.n%)	nn (nn.n%)	nn (nn.n%)	nn (nn.n%)	nn (nn.n%)	nn (nn.n%)	nn (nn.n%)	nn (nn.n%)	nn (nn.n%)	nn (nn.n%)
	6	nn (nn.n%)	nn (nn.n%)	nn (nn.n%)	nn (nn.n%)	nn (nn.n%)	nn (nn.n%)	nn (nn.n%)	nn (nn.n%)	nn (nn.n%)	nn (nn.n%)
	7	nn (nn.n%)	nn (nn.n%)	nn (nn.n%)	nn (nn.n%)	nn (nn.n%)	nn (nn.n%)	nn (nn.n%)	nn (nn.n%)	nn (nn.n%)	nn (nn.n%)
8+	nn (nn.n%)	nn (nn.n%)	nn (nn.n%)	nn (nn.n%)	nn (nn.n%)	nn (nn.n%)	nn (nn.n%)	nn (nn.n%)	nn (nn.n%)	nn (nn.n%)	
B N = x	0	nn (nn.n%)	nn (nn.n%)	nn (nn.n%)	nn (nn.n%)	nn (nn.n%)	nn (nn.n%)	nn (nn.n%)	nn (nn.n%)	nn (nn.n%)	nn (nn.n%)
	1	nn (nn.n%)	nn (nn.n%)	nn (nn.n%)	nn (nn.n%)	nn (nn.n%)	nn (nn.n%)	nn (nn.n%)	nn (nn.n%)	nn (nn.n%)	nn (nn.n%)
	2	nn (nn.n%)	nn (nn.n%)	nn (nn.n%)	nn (nn.n%)	nn (nn.n%)	nn (nn.n%)	nn (nn.n%)	nn (nn.n%)	nn (nn.n%)	nn (nn.n%)
	3	nn (nn.n%)	nn (nn.n%)	nn (nn.n%)	nn (nn.n%)	nn (nn.n%)	nn (nn.n%)	nn (nn.n%)	nn (nn.n%)	nn (nn.n%)	nn (nn.n%)
	4	nn (nn.n%)	nn (nn.n%)	nn (nn.n%)	nn (nn.n%)	nn (nn.n%)	nn (nn.n%)	nn (nn.n%)	nn (nn.n%)	nn (nn.n%)	nn (nn.n%)

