	5	nn (nn.n%)	nn (nn.n%)	nn (nn.n%)	nn (nn.n%)	nn (nn.n%)	nn (nn.n%)	nn (nn.n%)	nn (nn.n%)	nn (nn.n%)	nn (nn.n%)
	6	nn (nn.n%)	nn (nn.n%)	nn (nn.n%)	nn (nn.n%)	nn (nn.n%)	nn (nn.n%)	nn (nn.n%)	nn (nn.n%)	nn (nn.n%)	nn (nn.n%)
	7	nn (nn.n%)	nn (nn.n%)	nn (nn.n%)	nn (nn.n%)	nn (nn.n%)	nn (nn.n%)	nn (nn.n%)	nn (nn.n%)	nn (nn.n%)	nn (nn.n%)
8+	nn (nn.n%)	nn (nn.n%)	nn (nn.n%)	nn (nn.n%)	nn (nn.n%)	nn (nn.n%)	nn (nn.n%)	nn (nn.n%)	nn (nn.n%)	nn (nn.n%)	

Baseline is defined as: Visit 2 in the MIV-711-201 study for Group A and Group B

[1] for each examination test, the summary will consider all possible subregions associated with Cartilage Assessment. Maximum number of subregions is 14. In this analysis a subregion is said to be affected by cartilage if the MRI score > 0. A subregion is not affected by cartilage if that subregion is scored as 0.

PAREXEL International SAP Amendment Shells

Medivir
Protocol: MIV-711-202

Final 1.0
16 January 2018

Medivir
Protocol Number: MIV-711-202

Page X of Y

Programming note: Similar table will be created:
Table 14.2.2.3 Imaging variables - MOAKS Cartilage Assessments Percentage of Full Thickness Loss Shift from Baseline to Visit 5 Number of
Subregions Impacted by MRI Feature, ITT Population

PAREXEL International SAP Amendment Shells

Medivir
Protocol: MIV-711-202

Final 1.0
16 January 2018

Medivir
Protocol Number: MIV-711-202

Page X of Y

Table 14.2.2.4
Imaging variables - MOAKS Osteophyte Size
Shift from Baseline to Visit 5 Number of Subregions Impacted by MRI Feature, ITT Population

Group	Number of subregions affected [1]	Baseline												
		0	1-3	4-5	6	7	8	9	10	11	12			
A	0	nn (nn.n%)	nn (nn.n%)	nn (nn.n%)	nn (nn.n%)	nn (nn.n%)	nn (nn.n%)	nn (nn.n%)	nn (nn.n%)	nn (nn.n%)	nn (nn.n%)	nn (nn.n%)	nn (nn.n%)	
	1-3	nn (nn.n%)	nn (nn.n%)	nn (nn.n%)	nn (nn.n%)	nn (nn.n%)	nn (nn.n%)	nn (nn.n%)	nn (nn.n%)	nn (nn.n%)	nn (nn.n%)	nn (nn.n%)	nn (nn.n%)	
	4-5	nn (nn.n%)	nn (nn.n%)	nn (nn.n%)	nn (nn.n%)	nn (nn.n%)	nn (nn.n%)	nn (nn.n%)	nn (nn.n%)	nn (nn.n%)	nn (nn.n%)	nn (nn.n%)	nn (nn.n%)	
	6	nn (nn.n%)	nn (nn.n%)	nn (nn.n%)	nn (nn.n%)	nn (nn.n%)	nn (nn.n%)	nn (nn.n%)	nn (nn.n%)	nn (nn.n%)	nn (nn.n%)	nn (nn.n%)	nn (nn.n%)	
	7	nn (nn.n%)	nn (nn.n%)	nn (nn.n%)	nn (nn.n%)	nn (nn.n%)	nn (nn.n%)	nn (nn.n%)	nn (nn.n%)	nn (nn.n%)	nn (nn.n%)	nn (nn.n%)	nn (nn.n%)	
	8	nn (nn.n%)	nn (nn.n%)	nn (nn.n%)	nn (nn.n%)	nn (nn.n%)	nn (nn.n%)	nn (nn.n%)	nn (nn.n%)	nn (nn.n%)	nn (nn.n%)	nn (nn.n%)	nn (nn.n%)	

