	9	nn (nn.n%)	nn (nn.n%)	nn (nn.n%)	nn (nn.n%)	nn (nn.n%)	nn (nn.n%)	nn (nn.n%)	nn (nn.n%)	nn (nn.n%)	nn (nn.n%)	nn (nn.n%)	nn (nn.n%)	
	10	nn (nn.n%)	nn (nn.n%)	nn (nn.n%)	nn (nn.n%)	nn (nn.n%)	nn (nn.n%)	nn (nn.n%)	nn (nn.n%)	nn (nn.n%)	nn (nn.n%)	nn (nn.n%)	nn (nn.n%)	
	11	nn (nn.n%)	nn (nn.n%)	nn (nn.n%)	nn (nn.n%)	nn (nn.n%)	nn (nn.n%)	nn (nn.n%)	nn (nn.n%)	nn (nn.n%)	nn (nn.n%)	nn (nn.n%)	nn (nn.n%)	
	12	nn (nn.n%)	nn (nn.n%)	nn (nn.n%)	nn (nn.n%)	nn (nn.n%)	nn (nn.n%)	nn (nn.n%)	nn (nn.n%)	nn (nn.n%)	nn (nn.n%)	nn (nn.n%)	nn (nn.n%)	
	B	0	nn (nn.n%)	nn (nn.n%)	nn (nn.n%)	nn (nn.n%)	nn (nn.n%)	nn (nn.n%)	nn (nn.n%)	nn (nn.n%)	nn (nn.n%)	nn (nn.n%)	nn (nn.n%)	nn (nn.n%)
		1-3	nn (nn.n%)	nn (nn.n%)	nn (nn.n%)	nn (nn.n%)	nn (nn.n%)	nn (nn.n%)	nn (nn.n%)	nn (nn.n%)	nn (nn.n%)	nn (nn.n%)	nn (nn.n%)	nn (nn.n%)
4-5		nn (nn.n%)	nn (nn.n%)	nn (nn.n%)	nn (nn.n%)	nn (nn.n%)	nn (nn.n%)	nn (nn.n%)	nn (nn.n%)	nn (nn.n%)	nn (nn.n%)	nn (nn.n%)	nn (nn.n%)	
6		nn (nn.n%)	nn (nn.n%)	nn (nn.n%)	nn (nn.n%)	nn (nn.n%)	nn (nn.n%)	nn (nn.n%)	nn (nn.n%)	nn (nn.n%)	nn (nn.n%)	nn (nn.n%)	nn (nn.n%)	
7		nn (nn.n%)	nn (nn.n%)	nn (nn.n%)	nn (nn.n%)	nn (nn.n%)	nn (nn.n%)	nn (nn.n%)	nn (nn.n%)	nn (nn.n%)	nn (nn.n%)	nn (nn.n%)	nn (nn.n%)	
8		nn (nn.n%)	nn (nn.n%)	nn (nn.n%)	nn (nn.n%)	nn (nn.n%)	nn (nn.n%)	nn (nn.n%)	nn (nn.n%)	nn (nn.n%)	nn (nn.n%)	nn (nn.n%)	nn (nn.n%)	
9		nn (nn.n%)	nn (nn.n%)	nn (nn.n%)	nn (nn.n%)	nn (nn.n%)	nn (nn.n%)	nn (nn.n%)	nn (nn.n%)	nn (nn.n%)	nn (nn.n%)	nn (nn.n%)	nn (nn.n%)	
10		nn (nn.n%)	nn (nn.n%)	nn (nn.n%)	nn (nn.n%)	nn (nn.n%)	nn (nn.n%)	nn (nn.n%)	nn (nn.n%)	nn (nn.n%)	nn (nn.n%)	nn (nn.n%)	nn (nn.n%)	

Baseline is defined as: Visit 2 in the MIV-711-201 study for Group A and Group B

[1] the summary will consider all possible subregions associated with osteophyte assessment. Maximum number of subregions is 12. In this analysis a subregion is said to be affected by an osteophyte if the MRI score > 0. A subregion is not affected by an osteophyte if that subregion is scored as 0.

PAREXEL International SAP Amendment Shells

Medivir
Protocol: MIV-711-202

Final 1.0
16 January 2018

Medivir
Protocol Number: MIV-711-202

Page X of Y

Table 14.2.3.1
NRS Scores Observed and Change from Baseline Summary
ITT Population

Parameter = How Active the target knee arthritis has been

Visit	Statistic	Group A N = x		Group B N = x	
		Observed N = x	Change N = x	Observed N = x	Change N = x
	n	nn		nn	
Visit 2	Mean	xx.x		xx.x	xx.x
MIV-711-201	SD	xx.xx		xx.xx	xx.xx

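### The MOAKS counting rule treats code 9 (not evaluable) as an affected subregion, and the resulting counts cannot show grade change where a subregion is already affected

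*SAP*

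**What the plan says.** SAP 8.2 lists the MOAKS codes. Size of cartilage loss ends with "3='>75% Area', 9='Not Evaluable", and percentage full-thickness loss is coded in the same way. Osteophytes are given as "Osteophytes (12 regions): 0='None', 1='Small', 2='Medium', 3='Large', 9='Not Evaluable". No code 9 is listed for bone marrow lesions (BML).

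The section then defines what is counted: "A subregion/location is considered to be by the MRI feature if it has score =1 or higher". A word is missing, but the footnotes in section 14 (Table Shells) make the meaning clear. Table 14.2.2.2: "In this analysis a subregion is said to be affected by cartilage if the MRI score > 0". Table 14.2.2.4: "In this analysis a subregion is said to be affected by an osteophyte if the MRI score > 0". Both footnotes give a score of 0 as the only unaffected state. Table 14.2.2.3 reuses the cartilage shell: "MOAKS Cartilage Assessments Percentage of Full Thickness Loss Shift from Baseline to Visit 5". For Table 14.2.2.1 the programming note says "table will include summaries for each MOAKS test: Number of BMLs, Size of BML, % that is BML".

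Each table cross-classifies patients by number of affected subregions at baseline and at Visit 5. The general rule on missing data in SAP section 6 is "Safety and efficacy data that are reported as missing will be excluded from all descriptive and non-descriptive data analysis".

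**The concern.** A 9 satisfies both forms of the rule, 1 or higher and above 0. Followed literally, an unreadable subregion is reported as diseased. If it was graded 0 at the other visit, the table shows a change that nobody observed.

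The second problem is separate. Each subregion is reduced to affected or not affected before counting, so a cartilage subregion that goes from the smallest grade of loss to the largest leaves the table as it was.

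MOAKS is one of four secondary objectives for Group A (Protocol 3.2, SAP 2.2) and exploratory for Group B. Tables 14.2.2.1 to 14.2.2.4 are its only planned summary. The quantitative MRI summaries in SAP 8.1 cover medial femur bone area, central medial cartilage thickness and total BML volume. They do not cover osteophytes or the remaining cartilage subregions.

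**Working it through.** The plan gives no figure to reproduce, and Protocol 9.2.1 states that the study is not powered for confirmatory analysis. The check applies the written rule to every listed code.

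**Inputs.** Codes 0, 1, 2, 3 and 9 for the two cartilage variables and osteophytes (SAP 8.2). Affected means score ≥ 1. There are 15 BML, 14 cartilage and 12 osteophyte sites (SAP 4.5.2). Shell categories: BML 0 to 4 singly, then 5+; cartilage 0 to 7 singly, then 8+; osteophytes 0, 1-3, 4-5, then 6 to 12 singly.

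**1. Codes flagged.** The rule flags 1, 2, 3 and 9; only 0 is unaffected. A wholly unreadable knee would score 14 of 14 for cartilage and 12 of 12 for osteophytes.

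**2. Moves involving code 9.** There are 8 ordered moves (four into 9, four out of it). Change in the patient's count:

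| Move | Rule as written | Drop 9 separately at each visit | Count only sites evaluable at both visits |
|---|---|---|---|
| 0 to 9 | +1 | 0 | 0 |
| 9 to 0 | −1 | 0 | 0 |
| 1, 2 or 3 to 9 | 0 | −1 | 0 |
| 9 to 1, 2 or 3 | 0 | +1 | 0 |

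The written rule gives an unobserved change in 2 of the 8 moves. Dropping 9 visit by visit gives one in the other 6. Only pairing removes all of them.

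**3. Effect on the table cell.** One extra affected site moves a patient up a category at every cartilage count from 0 to 7, and at osteophyte counts 0, 3, 5, 6, 7, 8, 9, 10 and 11, which is 9 of the 12 possible starting counts (0 to 11).

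**4. Examples.** Baseline: 6 affected cartilage subregions and 8 at grade 0.
- Two of the grade 0 subregions become 9 at Visit 5. As written: 6 to 6 + 2 = 8, shown as 6 to 8+. Paired, on 14 − 2 = 12 subregions: 6 to 6.
- Instead, two of the affected subregions become 9. As written: 6 to 6. Dropping 9 per visit: 6 to 6 − 2 = 4, an apparent improvement. Paired: 4 to 4.

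**5. Grade change.** Grades 0 to 3 allow 4 × 3 = 12 ordered moves. Six leave the count unchanged: 1 to 2, 1 to 3, 2 to 1, 2 to 3, 3 to 1 and 3 to 2. Three subregions going from grade 1 to grade 3 are tabulated as 3 to 3. One site going 0 to 1 while another goes 1 to 0 also gives no shift.

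**6. Open categories.** For BML, 5+ holds counts 5 to 15, which is 11 of 16 possible values. For cartilage, 8+ holds 8 to 14, which is 7 of 15. The osteophyte table has no open category.

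**7. How often code 9 might occur.** The documents give no rate. As an assumption, let each site be unreadable with probability q, independently. The chance of at least one 9 at a visit is 1 − (1 − q)^k, with k the number of sites:

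| q | 14 cartilage sites | 12 osteophyte sites |
|---|---|---|
| 1% | 13% | 11% |
| 2% | 25% | 21% |
| 5% | 51% | 46% |
| 10% | 77% | 72% |

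These are chances of meeting a 9, not of a false shift; under the written rule the site must also be graded 0 at the other visit.

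**The case against.** The label of code 9 says that no grade was given, and SAP section 6 excludes missing data and forbids imputation. A sensible programmer might well set 9 to missing, and the MOAKS listings print the score text, so a 9 could be seen on review. This does not settle the matter. Code 9 is a reported, labelled value, the explicit rule and footnotes point the other way, and dropping it visit by visit creates false shifts of the opposite kind (step 2).

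The size is not shown. This stands. Protocol 7.8 requires quality control of each image set, allows a repeat MRI, and fixes the scanner and coil, so code 9 may be rare. Where the unreadable site was affected at the other visit, the written rule gives no false shift.

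Counting affected subregions is a legitimate, openly stated descriptive summary. Grades stay in the by-patient listings, Table 14.2.2.3 shows new full-thickness loss separately, and cartilage thickness and BML volume are modelled as continuous outcomes. This stands too: the grade-change point is a limit of the summary, not an error in it.

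Finally, the text of SAP 8.2 plans shift tables for three variables only: number of BMLs and cysts, size of cartilage loss, and osteophytes. Full-thickness loss, BML size and the BML percentage come in through the shells, although Table 14.2.2.3 is also in the SAP's own list of tables. Number of BMLs is a lesion count, not a 0 to 3 grade, so the figure of 6 in 12 does not describe it.

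**Conclusion.** The concern holds. For Tables 14.2.2.2 to 14.2.2.4 the rule is wrong as written, because it counts an unreadable subregion as affected. Table 14.2.2.1 is untouched by this part, since BML lists no code 9. The second part also holds: counts of affected sites cannot show grade change within an affected site, and the open categories in the BML and cartilage tables hide some changes in the count itself.

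The figures above are numbers of possible cases, not expected frequencies; the real effect depends on how often code 9 and within-grade change occur, which the documents do not give. The tables are descriptive, so no error rate is at stake. What is at stake is whether the only summary of a secondary objective reports change correctly. The code 9 rule should be corrected; the grade-change rows are a cheap improvement to add at the same time.

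**What to change.** - In SAP 8.2 and the footnotes of Tables 14.2.2.2 to 14.2.2.4, state that code 9 is missing, that affected means a score of 1, 2 or 3, and that only subregions evaluable at both baseline and Visit 5 are counted. Report the number not evaluable by group and visit.
- For the graded variables (BML size, size of cartilage loss, full-thickness loss, osteophytes), add per patient the number of subregions that worsened, and the number that improved, by at least one grade from baseline to Visit 5.
- In Tables 14.2.2.1 to 14.2.2.3, add the change in count or remove the open 5+ and 8+ categories.
- Bring the variables named in the text of SAP 8.2 into line with those in the shells.

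The cost is a sentence or two in SAP 8.2, three footnotes and some extra table rows. All scores are already collected and listed. The tables become longer, and a patient contributes slightly fewer subregions where one cannot be read at one of the visits.

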### 7.2 Secondary Endpoints (Study Population A)

Bone parameters will be measured from MRIs of the bone area taken at Visit 2 (Enrolment) and Visit 8 of Study MIV-711-201 as well as the MRI of the bone area taken at Visit 5 in Study MIV-711-202.

MRIs will be analysed semi-quantitatively by a central experienced musculoskeletal radiologist using the MOAKS [36] and quantitatively using statistical shape modelling (SSM, Imorphics Ltd) for the features below. [23, 37, 38]

MOAKS scoring will be used to assess the following features:

- Bone marrow lesions (BMLs) and cysts: 15 sub-regions graded for BML (including ill-defined lesions and cysts) size in regard to the total volume of the sub-region occupied by BML(s). Grade 0=none, grade 1<33% of sub-regional volume, grade 2=33–66% of sub-regional volume and grade 3>66% of sub-regional volume.
- Articular cartilage: 14 articular cartilage regions graded for size of any cartilage loss (including partial and full thickness loss) as a % of surface area as related to the size of each individual region surface and % of loss in this sub-region that is full-thickness loss.
- Osteophytes: 12 sites scored for presence and size of osteophytes. Grade 0=none; Grade 1=small; Grade 2= medium; Grade 3= large.

Bone shape modelling of MRI will be used to assess:

- Mean cartilage thickness (mm) for each of the anterior, posterior and central regions, with areas denuded of cartilage included as having zero thickness [39]
- Bone marrow lesion volume (mm^3) by anatomical region: medial and lateral femorotibial region of femur, medial and lateral patellofemoral region of femur, medial and lateral tibia, and patella
- Bone area (mm^2) for anatomical regions: lateral and medial femur (patellofemoral); lateral and medial femur (femorotibial); lateral and medial patella, lateral and medial tibial condyle
- Bone shape by distance along an OA shape vector for femur, tibia and patella
- Index bone area/cartilage thickness.

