#### 9.5.2.2 Study Population A

The secondary endpoints are related to efficacy:

- The effect of MIV-711 on MRI cartilage thickness loss
- The effect of MIV-711 on MRI bone marrow lesion volume
- The effect of MIV-711 in the semi quantitative MRI Osteoarthritis Knee Score (MOAKS) parameters
- To assess the effect of MIV-711 on MRI knee joint bone area.

Note: all MRI assessments refer to the target knee unless stated otherwise.

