4.5.2 MRI MOAKS

MRIs will be analysed semi-quantitatively by a central musculoskeletal radiologist using the MOAKS.

MOAKS scoring will be used to assess the following features:

- Bone marrow lesions (BMLs) and cysts
- Articular cartilage
- Osteophytes

MRI assessment using MOAKS scoring will be used to assess the following features, as provided by PAREXEL MRI:

- Bone Marrow Lesions (BMLs) and cysts. This involves 15 subregions graded for BML size (including ill-defined lesion and cysts) measuring the total volume of the subregion occupied by BML(s). Grade 0= none, grade 1 < 33% of subregional volume, grade 2 = 33 to 66% of subregional volume and grade 3 > 66% of subregional volume.
- Articular Cartilage: This involves 14 articular cartilage regions graded for size of any cartilage loss (including partial and full thickness loss) as a percentage of surface area as related to the size of each individual region surface and percentage of loss in this subregion that is full-thickness loss.
- Osteophytes: This involves 12 sites scored for presence and size of osteophytes. Grade 0=none, Grade 1= small, Grade 2 = medium, Grade 3 = large.

The specific subregions associated with the above three groups of MOAKS scoring are outlined in the table below:

Bone Marrow Lesions (BMLs) and cysts	Articular Cartilage	Osteophytes
Medial Patella	Medial Patella	Superior Patella
Lateral Patella	Lateral Patella	Inferior Patella
Medial Femur Trochlea	Medial Femur Trochlea	Medial Patella

PAREXEL International Statistical Analysis Plan

Medivir
Protocol: MIV-711-202

Final 1.0
16 January 2018

Medial Femur Central	Medial Femur Central	Lateral Patella
Medial Femur Posterior	Medial Femur Posterior	Medial Femur Trochlea
Lateral Femur Trochlea	Lateral Femur Trochlea	Medial Femur Central
Lateral Femur Central	Lateral Femur Central	Medial Femur Posterior
Lateral Femur Posterior	Lateral Femur Posterior	Lateral Femur Trochlea
Medial Tibia Anterior	Medial Tibia Anterior	Lateral Femur Central
Medial Tibia Central	Medial Tibia Central	Lateral Femur Posterior
Medial Tibia Posterior	Medial Tibia Posterior	Tibia Medial
Subspinous	Lateral Tibia Anterior	Tibia Lateral
Lateral Tibia Anterior	Lateral Tibia Central	
Lateral Tibia Central	Lateral Tibia Posterior	
Lateral Tibia Posterior		

Bone Marrow Lesions (BMLs) and cysts: The 15 subregions will be assessed for:

- Size of BML
- Number of BMLs
- Percentage that is BML

Articular Cartilage: The 14 subregions will be assessed for:

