Table 14.2.1.2	Imaging variables - MRI of Cartilage Thickness for the Target Knee Observed and Change from Baseline Summary, ITT Population
Table 14.2.1.3	Imaging variables - MRI of Total BML Volume for the Target Knee Observed and Change from Baseline Summary, ITT Population
Table 14.2.1.4	Imaging variables - MRI of Bone Area for the Target Knee Observed and Change from Baseline Summary, PPS Population
Table 14.2.1.5	Imaging variables - MRI of Cartilage Thickness for the Target Knee Observed and Change from Baseline Summary, PPS Population
Table 14.2.1.6	Imaging variables - MRI of Total BML Volume for the Target Knee Observed and Change from Baseline Summary, PPS Population
Table 14.2.1.7	Statistical Analysis – MRI of Bone Area for the Target Knee in Patients with Moderate Osteoarthritis, ITT Population
Table 14.2.1.8	Statistical Analysis - MRI of Cartilage Thickness for the Target Knee in Patients with Moderate Osteoarthritis, ITT Population
Table 14.2.1.9	Statistical Analysis - MRI of Total BML Volume for the Target Knee in Patients with Moderate Osteoarthritis, ITT Population
Table 14.2.2.1	Imaging variables - MOAKS Bone Marrow Lesion (BML) and Cyst Shift from Baseline to Visit 5 Number of Subregions Impacted by MRI Feature, ITT Population
Table 14.2.2.2	Imaging variables - MOAKS Cartilage Assessments Size of any Cartilage Loss Shift from Baseline to Visit 5 Number of Subregions Impacted by MRI Feature, ITT Population
Table 14.2.2.3	Imaging variables - MOAKS Cartilage Assessments Percentage of Full Thickness Loss Shift from Baseline to Visit 5 Number of Subregions Impacted by MRI Feature, ITT Population
Table 14.2.2.4	Imaging variables - MOAKS Osteophyte Size Shift from Baseline to Visit 5 Number of Subregions Impacted by MRI Feature, ITT Population

PAREXEL International Statistical Analysis Plan

Medivir
Protocol: MIV-711-202

Final 1.0
16 January 2018

Table 14.2.3.1	NRS Scores Observed and Change from Baseline Summary, ITT Population
Table 14.2.3.2	Statistical Analysis of NRS Scores, ITT Population
Table 14.2.4.1	Normalized WOMAC Scores Observed and Change from Baseline Summary - ITT Population
Table 14.2.4.2	Individual WOMAC Scores Observed and Change from Baseline Summary, ITT Population
Table 14.2.4.3	Statistical Analysis – Normalized WOMAC Scores, ITT Population
Table 14.2.4.4	Statistical Analysis – WOMAC Pain Score (walking on a flat surface), ITT Population

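### The MOAKS secondary endpoint is summarised only as a net count of affected subregions, so grade changes that stay at 1 or above do not show in its tables

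*SAP*

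**What the plan says.** Protocol 9.5.2.2 lists among the secondary efficacy endpoints for Study Population A "The effect of MIV-711 in the semi quantitative MRI Osteoarthritis Knee Score (MOAKS) parameters". Protocol 7.4.2 makes the same parameters exploratory for Study Population B.

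The data are ordinal grades by subregion (Protocol 7.2, SAP 4.5.2 and 8.2):

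- BML size in 15 subregions, where for example "grade 2 = 33 to 66% of subregional volume and grade 3 > 66% of subregional volume".
- Osteophytes at 12 sites: "Grade 0=none; Grade 1=small; Grade 2= medium; Grade 3= large".
- Cartilage loss in 14 regions, coded in SAP 8.2 as "Size of any Cartilage Loss: 0='Normal', 1='<10% Area', 2='10-75% Area', 3='>75% Area', 9='Not Evaluable", with a parallel code for full-thickness loss.

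SAP 8.2 lists the scores for each patient. It then counts, per patient and visit, the subregions scoring 1 or higher for three variables: number of BMLs and cysts, size of cartilage loss, and osteophytes. The only summary is built on that count: "Shift tables by group will be tabulated for the shift from baseline to visit 5 for the number of subregions impacted by the MRI feature".

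The shells in SAP 14 apply the same cut, written as a score above 0:

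- Table 14.2.2.1 adds BML size and percentage that is BML. Its footnote says "Maximum number of subregions is 15", and its columns stop at 5+.
- Table 14.2.2.2 (size of cartilage loss) says "Maximum number of subregions is 14", and its columns stop at 8+.
- Table 14.2.2.3 repeats that layout for full-thickness loss.
- Table 14.2.2.4, titled in SAP 11 "MOAKS Osteophyte Size Shift from Baseline to Visit 5 Number of Subregions Impacted by MRI Feature", has columns 0, 1-3 and 4-5, then single columns from 6 to 12.

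**The concern.** The instrument records how large each lesion is. The summary records only whether a lesion is there, and then nets the result over the knee. The tables named for the size of cartilage loss and of osteophytes therefore contain no information on size beyond zero or not zero.

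The patients have symptomatic, radiographic knee OA, so some subregions are presumably affected at entry. In those subregions, the changes open to the drug or the disease are mostly changes of grade. A table with all patients on the diagonal could be read as structural stability on a secondary endpoint although grades had moved. In a descriptive study no test stands behind the table, so the table is the result.

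**Working it through.** The plan gives no power, sample size or target effect for MOAKS (Protocol 9.2.1 says the study is not powered for confirmatory analyses), so there is no figure of its own to reproduce. What can be checked is which changes the rule registers. The counts below enumerate possible values. They do not estimate how often the changes occur.

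**Inputs.** Grades 0-3, cut at 1 or higher (SAP 8.2 and the shells); maximum counts 15, 14 and 12; category limits from Tables 14.2.2.1, 14.2.2.2 and 14.2.2.4.

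**1. One subregion.** There are 4 × 4 = 16 pairs of baseline and Visit 5 grades, of which 4 are unchanged, leaving 12 changes. Those that cross the cut are 0 to 1, 2 or 3 and the reverse: 3 + 3 = 6. Those that stay at 1 or above are 1-2, 1-3 and 2-3 in both directions: 6. So 6 of 12 are hidden.

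**2. A subregion already affected at baseline.** There are 3 starting grades × 3 other grades = 9 changes. Three are worsening (1 to 2, 1 to 3, 2 to 3), and none shows. Six are improving, and the 3 that end at grade 0 show. So 3 of 9 are visible.

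**3. Cancellation.** The change in count equals new minus resolved subregions. Three new and three resolved give 3 − 3 = 0, and a patient starting at 3 is tabulated as 3 to 3.

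**4. Pooling.** With n possible counts there are n(n − 1) ordered changes, and a category pooling k counts hides k(k − 1) of them.

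| Feature | Possible counts | Pooled categories | Changes hidden |
|---|---|---|---|
| BML | 0-15, n = 16 | 5+ holds 5-15, k = 11 | 11 × 10 = 110 of 16 × 15 = 240 |
| Cartilage | 0-14, n = 15 | 8+ holds 8-14, k = 7 | 7 × 6 = 42 of 15 × 14 = 210 |
| Osteophytes | 0-12, n = 13 | 1-3 and 4-5 only; top category is 12 alone | 3 × 2 + 2 × 1 = 8 of 13 × 12 = 156 |

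**5. Example patients.**

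- All 14 cartilage regions go from grade 1 to grade 3: the count is 14 to 14, tabulated as 8+ to 8+.
- Three BML subregions shrink from grade 3 to grade 1: 3 to 3.
- BML spreads from 5 to 15 subregions: 5+ to 5+.
- Osteophytes go from 11 to 12 sites: 11 to 12, visible.

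**6. Two details of the rule.** For BML, the 0-3 enumeration applies to lesion size, which enters through the shell's programming note. The variable named in SAP 8.2 is a number of lesions with no 0-3 scale given, but the same cut hides any change there that stays at 1 or more. Also, code 9 (not evaluable) literally satisfies a score of 1 or higher: two cartilage regions going from 0 to 9 would move the count from 0 to 2.

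**The case against.** The strongest reply is that lesion size is measured better elsewhere. SAP 8.1 and 8.1.1 summarise and model total BML volume and central medial femur and tibia cartilage thickness, and a BML shrinking from grade 3 to 1 would be expected to register in total volume. That stands, and it narrows the point. It does not close it. SAP 8.1 summarises no measure of osteophyte size, and the lateral, trochlear and patellar cartilage measures appear only in listings.

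A reader might infer that change in an existing lesion can never show. The documents do not support that: resolution to grade 0 lowers the count, and a cartilage region with partial loss that first develops full-thickness loss moves from 0 to 1 or higher in Table 14.2.2.3. Nor are all the shells capped at the top, since the osteophyte columns run to the maximum of 12.

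It is also fair to say that the documents give no baseline MOAKS distribution. The statement that many subregions are affected at entry is therefore an assumption, and the fractions above weight all transitions equally.

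Finally, Protocol 9.5.2.4 asks only for descriptive summaries and prescribes no particular one for MOAKS. No decision rule rests on it, and the raw grades stay in the listings. The plan therefore breaches nothing and loses no data. A listing, however, is not a summary of a secondary endpoint.

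**Conclusion.** The point holds in limited form. Within its own table, the planned summary misses 6 of the 12 possible grade changes in a subregion, including all 3 worsening moves from an affected state. It nets new against resolved subregions, and it hides changes within the 5+ category for BML and the 8+ category for cartilage. The loss matters most for osteophyte size and for cartilage outside the central medial regions.

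The enumeration follows from SAP 8.2 and the shells alone. Its practical weight depends on how many subregions are affected at baseline and how often grades move, and neither is in the documents. They therefore do not support a claim that the MOAKS tables will mislead, or that structural change goes unmeasured in this study. This is an inexpensive improvement to a descriptive, unpowered analysis; it does not invalidate the plan.

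**What to change.** In SAP 8.2 and the shells for Tables 14.2.2.1 to 14.2.2.4, add two numbers per patient for each graded feature (BML size, size of cartilage loss, full-thickness loss, osteophyte size): the subregions that worsened by at least one grade from baseline to Visit 5 and, separately, those that improved by at least one grade. Use only subregions evaluable at both visits, with code 9 treated as missing. Summarise descriptively by group and keep the existing shift tables as support.

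All 12 grade changes then show, and three new plus three resolved subregions read as 3 worsened and 3 improved.

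A sum of grades is best left out. If it is wanted, restrict it to subregions evaluable at both visits and label it supportive: otherwise a code 9 at one visit shifts the sum with no change in the knee, and the grades are ordinal with unequal widths.

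The baseline for Group B should be settled at the same time. SAP section 8 gives Visit 8 of MIV-711-201, while the footnotes of these shells give Visit 2 of that study.

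The grades are already in Listings 16.2.6.8.1, 16.2.6.8.2 and 16.2.6.8.6, so no new data are needed. The cost is a few extra descriptive rows to program and present.
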